### Study design:

This is a collaborative study developed by different health and research institutions. The group is composed by BCNatal (Barcelona Center for Maternal Fetal and Neonatal Medicine, *Hospital Sant Joan de Déu*), *Grupo de investigación Infancia y Entorno* (GRIE), Psychiatry Service of *Hospital Clínic de Barcelona* and the Health Department of Catalunya and ASSIR (*Centre d'Atenció a la Salut Sexual i Reproductiva*) of Baix Llobregat.

This is a cluster randomized simple masking controlled trial evaluating the effectiveness of repeated motivational interview (MI) during pregnancy on prevalence of ethanol intake, together with its effects on offspring neurodevelopment.

Data will be collected by the study-site manager and stored in an electronic data-capture database. The coordinator of the study and the statistician will witness the accuracy of the data at the beginning, middle, and end of the study (on-site audit). Data will be captured in a paper form basis and then captured into the electronic database.

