#### Prenatal procedures:

All participants will be followed-up during the pregnancy applying following procedures:

- Questionnaires to evaluate sociodemographic, health and habits background. This questionnaire will be answered during the first trimester of pregnancy.
- SCL-90 (Symptom Checklist): In order to evaluate mental health. This questionnaire will be filled during the first trimester of pregnancy.
- AUDIT-C (Assessment of the Alcohol use disorders identification test): To evaluate ethanol intake. This questionnaire will be filled during first trimester of pregnancy and also up to 7 days after delivery.
- Fetal neurosonography: To evaluate fetal neurodevelopment and brain structure at 28 and 32 weeks of gestation through transabdominal and transvaginal exploration using a General Electric Voluson E10 sonograph (GE Medical Systems, Zipf, Austria).
- Biological samples: Samples will be collected at the moment of delivery to obtain to different biomarkers :
  - o Ethylglucuronide (EtG) on mother's hair: In order to evaluate chronic ethanol intake.
  - o Phosphatidylethanol (PEtH) on dried cordblood spot: In order to evaluate ethanol intake during last 3 weeks prior delivery.

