#### Postnatal procedures:

After both groups (the experimental and control) have delivery, a postnatal follow-up to participants (mothers and children) will be given:

- Edinburgh postnatal depression scale (EPDS): This scale evaluates the presence of post-natal depression or anxiety. This questionnaire will be performed to mothers at 6 months from delivery.
- ASQ-3 (Ages and Stages Questionnaires): This parent-report questionnaire could be applied since first month until 5 years and a half of life. It includes 30 questions organized in 5 areas of develop (communication, gross motor, fine motor, problems-solving and adaptative skills). It will apply at 6 and 12 months of age.
- Infant Behavior Questionnaire Revised (IBQ-R): This questionnaire is a parent-report measure of infant temperament. It will be performed at 12 months from delivery.
- Bayley- III test: This test evaluate mental and motor development and also children behavior between 1 month to 42 months of age. It will be performed at 18 months of age.
- Canadian Guidelines for Diagnosis of FASD: It will be evaluated by a pediatrician at 18 months of age regarding the diagnostic criteria of FAS and FASD of Canadian Guidelines.

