### Randomization and intervention

Under a sequential rollout, 8 clusters (primary care centers from a geographic location of Barcelona; Baix Llobregat) were randomly allocated according to a random number generator with a fixed seed, using R Core Team (2018). R: A language and environment for statistical computing. R Foundation for Statistical Computing, Vienna, Austria. URL <https://www.R-project.org/>, to incorporate a MI program into existing prenatal care visits (intervention group) or usual intervention (control group). The allocation was performed by a statistician. Midwives from centers allocated to perform MI were trained by an expert team. Participants enrolment was performed by midwives of both groups (interventional and control group). This is a simple masking study, it means that participants will not aware of the allocation and intervention.

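### Masking is defined for participants only; none is provided for the sonographer, the Bayley-III examiner or the FASD pediatrician, whose judgement-based measures serve the neurodevelopment aim

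*Combined protocol and SAP*

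**What the plan says.** The Study design section introduces the trial in these words: "This is a cluster randomized simple masking controlled trial evaluating the effectiveness of repeated motivational interview (MI) during pregnancy on prevalence of ethanol intake". The same sentence adds a second aim: "together with its effects on offspring neurodevelopment". The Randomization and intervention section then says what the masking label means: "This is a simple masking study, it means that participants will not aware of the allocation and intervention". It also says that the units of allocation are 8 primary care centers, that midwives at the MI centers were trained, and that midwives in both arms enrolled the women.

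Three examiner-based assessments serve the neurodevelopment aim:

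- Under Prenatal procedures: "Fetal neurosonography: To evaluate fetal neurodevelopment and brain structure at 28 and 32 weeks of gestation through transabdominal and transvaginal exploration". The operator is not identified.
- Under Postnatal procedures, the Bayley-III at 18 months, described thus: "This test evaluate mental and motor development and also children behavior between 1 month to 42 months of age". The examiner is not identified.
- Also under Postnatal procedures, the FASD assessment: "It will be evaluated by a pediatrician at 18 months of age regarding the diagnostic criteria of FAS and FASD of Canadian Guidelines".

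None of these entries mentions masking. The Outcomes section names one primary outcome, measured by EtG in maternal hair and PEth in cord blood, and does not rank the neurodevelopment measures.

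**The concern.** The plan does more than leave masking unmentioned. It adopts a scheme, defines it, and gives it to one party. A team that follows the text as written has no instruction to keep arm or center from the people who scan the fetus, score the child or make the diagnosis.

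Three features of this trial make that matter. First, fetal brain imaging, a developmental test and a criteria-based diagnosis all depend in part on what the examiner decides. Secondly, with whole centers allocated, the name of the center on a form can stand in for the arm. Thirdly, the party that is masked is the hardest to mask: a woman counselled at least once each trimester knows that she is being counselled, even if she does not know that the trial compares this with usual care. The ASQ-3 and IBQ-R are completed by parents, so the examiner-rated measures are where masking can most realistically protect the neurodevelopment aim.

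If examiners' expectations shift their ratings, the shift is mixed with the treatment effect. Nothing in the Statistical analysis section would detect or remove it.

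**Working it through.** **Who is masked, role by role**

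| Role | Where in the plan | Masking stated |
|---|---|---|
| Participants | Randomization and intervention | Yes, by definition |
| Midwives at MI centers | Randomization and intervention | No; they are trained to deliver MI and so know the arm |
| Sonographer, 28 and 32 weeks | Prenatal procedures | None stated |
| Bayley-III examiner, 18 months | Postnatal procedures | None stated |
| FASD pediatrician, 18 months | Postnatal procedures | None stated |

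The plan also does not say where the three assessments take place, or whether assessors see the woman's center or prenatal record. The Study design section says that data go first onto paper forms; nothing says that center is kept off them.

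**What is exposed.** The primary outcome is a laboratory result that none of the three assessors rates. The exposed measures are those behind the neurodevelopment aim.

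**Illustration of size.** The plan gives no figure to reproduce for assessor bias, so this shows scale only.

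Inputs:
- 168 children completing follow-up (Sample size section: 240 × 0.70 = 168).
- An equal split, 84 per arm. This is an assumption; the section gives no split.
- Two-sided 5% test, critical value 1.96. The section gives 5%; two-sided is an assumption.
- A spurious shift d of 0.1 or 0.2 SD with no true effect. This is an assumption; the documents give no such value.
- Independent observations, that is, no clustering. This is a simplification.

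Formulas: λ = d / √(1/n₁ + 1/n₂), which for equal arms is d × √(n/2). The false-positive rate is P(Z > 1.96 − λ) + P(Z < −1.96 − λ).

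- d = 0.1: λ = 0.1 × √42 = 0.648; rate = 0.0948 + 0.0046 = 0.099, about 10%.
- d = 0.2: λ = 0.2 × √42 = 1.296; rate = 0.2534 + 0.0006 = 0.254, about 25%.

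**Sensitivity to the split.** The Sample size section speaks of exposed children, with prevalences of 40% and 25%. If the 168 divided in that ratio, the arms would be 168 × 40/65 ≈ 103 and 168 × 25/65 ≈ 65. Then λ = 0.631 and 1.263, and the rates are 0.097 and 0.243. The split hardly matters; the assumed shift drives the result.

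The calculation concerns a continuous score. It says nothing about the FASD diagnosis, which is categorical.

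**The case against.** The strongest reply is that silence is not evidence of knowledge. The plan does not say that any of the three assessors knows the allocation. They may work away from the primary care centers, never see the center's name, and be masked in practice. A reader might infer that the assessors are in fact unmasked; the documents do not support that. What stands is that the plan defines its masking and does not extend it to them, so no safeguard is in place on paper.

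A second reply is that the primary outcome is untouched. This is correct as far as these three assessors go. A reader might infer that the trial's main result is open to this bias, and the text gives no ground for that.

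A third concerns cost. It is tempting to say that masking the assessors would be free. The documents give no staffing, cost or logistics for the assessments, and relabelling forms and logging unmasking is work. Allocation and enrolment are also reported in the past tense, so some assessments may already have been done, and a change could protect only the rest.

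A fourth is that the 0.2 SD shift has no source in the plan. That is so, which is why a range is shown. It would also be wrong to read the 168 completers as 168 per arm: the Sample size section gives 168 as the number of children completing, and a calculation with 168 in each arm would double it and overstate the inflation.

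Finally, nothing places these assessors in the MI training team, which the plan describes as a psychiatrist and a psychologist. The concern does not depend on their having a stake in MI; it needs only that they could learn the arm.

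**Conclusion.** The concern holds in a limited form. The plan confines masking to participants and provides none for three assessors whose judgement-based measures serve a stated aim. Allocation of only 8 centers makes the arm easy to infer from the center. This is a weakness of the stated scheme and not merely a missing detail, because the scheme as written omits these assessors and a better one is available at small cost.

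Its reach is the neurodevelopment measures. Its size cannot be derived from the documents. Under the stated assumptions, a shift of 0.1 to 0.2 SD takes a nominal 5% error rate to about 10% to 25% on a continuous score. Those figures ignore clustering and should be read as an order of magnitude. The change is one that should be made; it does not call the biomarker comparison into question.

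**What to change.** Amend the Randomization and intervention section to say who is masked besides participants, and to what. Specifically:

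- Mask the existing sonographers, Bayley-III examiners and FASD pediatrician to both arm and center for all assessments still to be done.
- Use study numbers that do not encode the center, and remove center and arm from the assessment forms.
- Ask families not to mention any counselling to the assessor.
- Have assessors record any accidental unmasking, and report how often it occurred by arm.
- Describe participants as not told the comparison, instead of as unaware of the intervention.
- If assessors have been masked all along, say so and state how. If some assessments were done without masking, state which.

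The cost is relabelling of forms and a log of unmasking. No extra visits or assessors should be needed, on the assumption that the assessors are not the midwives who deliver MI; the plan does not say, and the team should confirm it. The limitation is that masking will sometimes fail when a family mentions counselling, and that assessments already completed cannot be protected.

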### Outcomes

The primary outcome of the study is to demonstrate the effectiveness of repetitive MI to reduce alcohol intake. This will be measured by the presence of ethanol intake biomarkers (EtG in mother's hair and Peth in cordblood).

### Statistical analysis

Analysis will be conducted by intention-to-treat. Missing data for the main outcome will be handled by complete data analysis because women without an answer on the main outcome will be excluded. All analyses will be divided by groups (control vs experimental group). Continuous data will be assessed for normality using the Kolmogorov-Smirnoff test. Normally distributed variables will be compared among groups using t-test and expressed as mean and standard deviation (SD), while not normally distributed variables will be compared using the Mann-Whitney-U test and expressed as medians and interquartile range (IQR). Quantitative variables will be compared using  $\chi^2$  test and expressed as counts (n) and proportions (%). For categorical variables Fisher exact test or Chi-squared test are used. Regarding demographic data (age, sex, body mass index (BMI), etc.); continuous variables will be presented as mean and SD, or median and IQR, according to their distribution, and categorical variables as percentages (%).

For the main outcome, differences in prevalence of ethanol intake between groups will be analyzed using absolute risk increase defined as the incidence of the outcome in the experimental group minus the incidence in the control group. The absolute risk increase will be depicted in a forest plot. A multivariate logistic regression will be performed to determine the Odds Ratio for ethanol intake adjusting by demographic characteristics. Data will be analyzed using R Core Team (2018). R: A language and environment for statistical computing. R Foundation for Statistical Computing, Vienna, Austria. URL <https://www.R-project.org/> and GraphPad Prism version 8.1.2, GraphPad Software, San Diego, California USA, [www.graphpad.com](http://www.graphpad.com).

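### For continuous secondary outcomes a normality pre-test chooses the comparison, and no between-group difference with a confidence interval, or allowance for the 8 centres, is planned

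*Combined protocol and SAP*

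**What the plan says.** All of the analysis rules are in the Statistical analysis section.

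- Pre-test: "Continuous data will be assessed for normality using the Kolmogorov-Smirnoff test". The plan gives no significance level. It does not say whether the test is run per arm or on pooled data, or whether it is corrected for a mean and SD estimated from the same sample.
- If judged normal: t-test, with mean and SD.
- Otherwise: "not normally distributed variables will be compared using the Mann-Whitney-U test", with median and IQR.
- Next sentence: "Quantitative variables will be compared using" a chi-squared test, shown as counts and proportions. A separate sentence then covers categorical data: "For categorical variables Fisher exact test or Chi-squared test are used".
- Main outcome: an "absolute risk increase defined as the incidence of the outcome in the experimental group minus the incidence in the control group", shown in a forest plot, plus an adjusted odds ratio.

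The section does not list the continuous outcomes. Postnatal procedures names EPDS at 6 months, ASQ-3 at 6 and 12 months, IBQ-R at 12 months and Bayley-III at 18 months. These would fall under the rule if analysed as scores. Of ASQ-3 the plan says "It includes 30 questions organized in 5 areas of develop", and it gives no scoring or range. The term confidence interval appears nowhere in the document.

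**The concern.** The t-test compares means and Mann-Whitney compares ranks, and the summaries that go with them differ too. When the data choose between them, the quantity being compared is not pre-specified. ASQ-3 could be reported as means at 6 months and as medians and ranks at 12 months, so the two visits could not be set side by side.

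A second gap matters more to the reader of the results. For continuous outcomes the plan yields group summaries and a p-value, with no estimate of the difference and no interval. The Study design section names effects on offspring neurodevelopment as part of what the trial evaluates. A non-significant p-value without an interval does not show which effects have been excluded.

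Third, both branches treat participants as independent, while the Randomization and intervention section says that 8 primary care centres were allocated.

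**Working it through.** No figure in the plan rests on this rule, so there is none to reproduce. The check asks how far the rule's result depends on things the plan leaves open.

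**Inputs.** Sample size section: about 240 children followed, 30% loss, so 240 × 0.70 = 168 completers, as stated. An equal split, 168 / 2 = 84 per arm, is an assumption. If the 168 are exposed children only, 40% against 25% with equal enrolment would give 168 × 40/65 ≈ 103 and 168 × 25/65 ≈ 65. The score distributions below and the 5% pre-test level are also assumptions, since the documents give neither.

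**Step 1: which branch is taken.** Share of simulated samples (1,000 per cell) judged non-normal:

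| n | Skewness 1, plain KS | Skewness 1, Lilliefors | Symmetric coarse score, plain KS | Symmetric coarse score, Lilliefors |
|---|---|---|---|---|
| 40 | 1.2% | 32.5% | 2.7% | 64.6% |
| 84 | 4.7% | 57.8% | 24.0% | 98.8% |
| 168 | 26.0% | 88.2% | 91.1% | 100% |
| 240 | 51.7% | 97.0% | 100% | 100% |

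The skewed population is a gamma with shape 4 (skewness 2/√4 = 1). The coarse score is a normal with SD 2 rounded to whole numbers. The simulation error is at most √(0.25/1,000) = 1.6 percentage points per cell, and repeat runs agree to within a few points. For truly normal data, plain KS flagged at most 0.1% and Lilliefors 3.6 to 5.1%, so the plain form is very conservative when mean and SD are estimated.

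Two things follow. One population goes to either branch depending on sample size, pooling and the version of the test. A symmetric score can also be flagged merely because its values are tied.

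**Step 2: one scale, two visits.** Suppose the population is the same at both visits and the samples are independent. The chance that the two visits get different tests is then 2p(1 − p), with p from the skewness-1 columns:

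- plain KS, n = 84: 2 × 0.047 × 0.953 = 9%
- plain KS, n = 168: 2 × 0.260 × 0.740 = 38%
- Lilliefors, n = 84: 2 × 0.578 × 0.422 = 49%
- Lilliefors, n = 168: 2 × 0.882 × 0.118 = 21%

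Scores from the same children are likely to be positively correlated, which would lower these figures.

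**Step 3: independence.** With 168 children in 8 centres, m = 168 / 8 = 21, and the design effect is 1 + (21 − 1) × ICC. The plan gives no ICC, so a range is assumed. The actual error of a nominal 5% test that ignores centre is approximately 2 × [1 − Φ(1.96/√design effect)].

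| Assumed ICC | Design effect | SE multiplier | Actual type I error |
|---|---|---|---|
| 0.01 | 1.20 | 1.10 | 7.4% |
| 0.02 | 1.40 | 1.18 | 9.8% |
| 0.05 | 2.00 | 1.41 | 16.6% |

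This applies to either branch, so removing the pre-test alone would not be enough.

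**The case against.** The strongest reply is that the pre-test does little harm to error rates. With identical distributions in both arms, 84 per arm and no clustering, the two-stage rule (plain KS per arm, then t-test or Mann-Whitney) had a type I error of 5.4% for the skewed population, 5.2% for a 13-level score with a ceiling and 5.1% for a log-normal. That stands. The case against the pre-test is an unspecified estimand and incomplete reporting.

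Three stronger readings are tempting, and the documents do not support them.

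- *That Mann-Whitney would produce false positives.* Take log-normals with equal means, log SDs of 0.7 and 0.5, and 84 per arm. Mann-Whitney rejects about 23 to 25% of the time and Welch's t-test 5 to 6%. But the distributions do differ: the log means are (0.49 − 0.25)/2 = 0.12 apart, with SE √((0.49 + 0.25)/84) = 0.094. A Welch test on logs therefore also rejects about 25% of the time (23.6% when simulated). This is a difference in estimand and not an error rate, and nothing in the plan suggests unequal spread.
- *That no effect estimate is planned anywhere.* The primary outcome is the presence of biomarkers. It has a defined risk difference, a forest plot (which normally shows an interval, though none is named) and an odds ratio. The pre-test does not touch it.
- *That scores would really be tested by chi-squared.* Counts and proportions follow in the same sentence, so the word is evidently a slip for qualitative. It needs correcting, but it does not change the analysis intended.

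**Conclusion.** The point holds for continuous secondary outcomes and descriptive comparisons, and it is a cheap improvement. It does not threaten the primary analysis. The reported comparison is chosen by a pre-test whose answer, for one assumed population with skewness 1, ranges from about 5% to 88% flagged according to the version used and whether 84 or 168 observations are tested. No difference with a confidence interval is planned for these outcomes, and neither test allows for the 8 centres.

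The missing estimate, the data-driven choice and the unmodelled centres are read directly from the text. The percentages are illustrations that rest on assumed distributions, an assumed 5% pre-test level, an assumed equal split and an assumed range of ICC. That the instruments will be analysed as scores is also an assumption, because the plan does not say.

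**What to change.** In the Statistical analysis section:

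1. Delete the normality pre-test and list the continuous outcomes with their time points.
2. For each scale score, pre-specify one difference in means (MI minus control) with a 95% confidence interval. Take it from a linear model that allows for centre with a small-number-of-clusters correction: for example a mixed model with a centre random effect and Kenward-Roger degrees of freedom, or a centre-level analysis. The plan defines no such method at present, so it has to be written in.
3. Keep rank-based tests as sensitivity analyses only.
4. If any biomarker concentration is analysed on the log scale, state that the estimand is a ratio of geometric means and how values below detection are handled.
5. In the chi-squared sentence, change quantitative to qualitative (categorical).

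The cost is SAP text and slightly more analysis work; no sample-size figure or trial procedure changes. Intervals will be wider. In a parallel comparison of 8 centres with 8 − 2 = 6 degrees of freedom, the t multiplier is 2.447 against 1.974 with 166. Combined with SE multipliers of 1.10 to 1.41, the intervals would be about 1.4 to 1.8 times as wide as those that ignore centre, for an ICC of 0.01 to 0.05.

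### Offspring outcomes get only crude between-arm tests by default, although baseline covariates are already collected; prespecified adjusted, centre-aware models would gain precision and correct realised imbalance

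*Combined protocol and SAP*

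**What the plan says.** The Study design section gives the trial two purposes: the effect of MI on ethanol intake, "together with its effects on offspring neurodevelopment". The offspring measures are listed under Prenatal procedures (neurosonography, "To evaluate fetal neurodevelopment and brain structure at 28 and 32 weeks of gestation") and Postnatal procedures (ASQ-3 at 6 and 12 months, IBQ-R at 12 months, Bayley-III and FASD assessment at 18 months).

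The Statistical analysis section mentions none of these measures. Its general rules are:

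- continuous and normal: "Normally distributed variables will be compared among groups using t-test and expressed as mean and standard deviation (SD";
- continuous and not normal: "not normally distributed variables will be compared using the Mann-Whitney-U test and expressed as medians and interquartile range (IQR";
- categorical: "For categorical variables Fisher exact test or Chi-squared test are used".

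The only adjusted model is for the main outcome: "A multivariate logistic regression will be performed to determine the Odds Ratio for ethanol intake adjusting by demographic characteristics". The covariates are not listed, and no method that accounts for centre is given for any outcome.

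Baseline data exist for all participants. Prenatal procedures lists "Questionnaires to evaluate sociodemographic, health and habits background" in the first trimester, together with SCL-90 and AUDIT-C. The Randomization and intervention section describes 8 centres allocated by a random number generator, with no stratification, matching or constraint, and enrolment by the midwives of both groups.

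**The concern.** With 8 randomised units, the arms can easily differ in social background, habits or maternal mental health, all plausible predictors of child development. A crude comparison leaves such a difference inside the estimate. It also leaves in the residual any outcome variation that the collected covariates could explain.

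The contrast between arms is likely to be diluted, because MI can alter a child's outcome only where it alters the mother's drinking. Avoidable noise therefore matters. The plan accepts adjustment in principle but confines it to ethanol intake. With no covariate list for the offspring outcomes, it also leaves covariates open to being chosen after the data are seen.

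**Working it through.** **Figures from the plan (Sample size section).** 240 children less 30% loss: 240 × 0.70 = 168, which reproduces. Assumed prevalence is 40% against 25%, a difference of 0.15. The stated 90% power concerns ethanol prevalence and is not used here. The plan gives no SD, intraclass correlation (ICC) or covariate R² for any offspring outcome.

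**Assumptions.** Score SD 15 within centre; 84 children per arm; 4 centres per arm, 21 children each; R² of 0.1 to 0.3; SD of centre means 0, 2 or 3 points.

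**1. No centre variation.** Crude SE = 15 × √(2/84) = 2.31 points. Adjusted SE = 2.31 × √(1 − R²); equivalent number = 168/(1 − R²).

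| R² | SE | Reduction | Equivalent children |
|---|---|---|---|
| 0.1 | 2.20 | 5% | 187 |
| 0.2 | 2.07 | 11% | 210 |
| 0.3 | 1.94 | 16% | 240 |

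**2. With centre variation, covariates explaining 30% of within-centre variance only.** Arm imbalance from centre means has SD = s × √(1/4 + 1/4), which is 1.41 for s = 2 and 2.12 for s = 3 (variances 2.0 and 4.5). The within-centre part is 2.31² = 5.36 crude and 0.7 × 5.36 = 3.75 adjusted.

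| s | Crude SE | Adjusted SE | Reduction | Variance ratio | 168 × ratio |
|---|---|---|---|---|---|
| 2 | √7.36 = 2.71 | √5.75 = 2.40 | 12% | 1.28 | 215 |
| 3 | √9.86 = 3.14 | √8.25 = 2.87 | 9% | 1.19 | 201 |

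The last column is relative efficiency, as if centres were added in proportion to children. On that scale, 240 is reached only if centre variance is nil or is also explained by the covariates.

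**3. Scale of the effect.** If exposure cost a child 7.5 points (assumed), the arm difference would be 0.15 × 7.5 = 1.1 points. Against SEs of 2.31 and 1.94, two-sided 5% power is about 8% and 9%.

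**4. Error rate, by simulation.** 4,000 runs per scenario, 8 centres of 21, no MI effect, one covariate.

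| Covariate ICC | R² | Residual ICC | Crude error | Adjusted error |
|---|---|---|---|---|
| 0 | 0.2 | 0 | 4.4% | 4.3% |
| 0.05 | 0.1-0.3 | 0 | 6.2-9.2% | 4.6-6.1% |
| 0.10 | 0.1-0.3 | 0 | 7.3-13.0% | 4.6-5.1% |
| 0.10 | 0.2 | 0.02 | 13.0% | 8.9% |
| 0.10 | 0.2 | 0.05 | 19.1% | 16.4% |

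Both analyses treat children as independent. The arms differed by more than 0.25 SD on the covariate in about 25% (ICC 0.05) or 35% (ICC 0.10) of allocations, against about 10% with no clustering.

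**5. Who the 168 are.** The Sample size section calls the followed children prenatally exposed. Read literally, with equal arms recruited, the split would be 168 × 0.40/0.65 = 103 to 168 × 0.25/0.65 = 65, not 84 to 84, and step 3 would not apply.

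**The case against.** The strongest case against the point has five parts.

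- **The plan does not expressly prescribe crude tests for child outcomes.** This is correct. They follow from a generic rule, because nothing more specific is written.
- **Chance imbalance does not invalidate a crude test.** A reader might infer that imbalance between centres produces false MI effects which adjustment would remove. The documents and the working do not support that. A valid cluster-level standard error already counts chance imbalance. The inflation in step 4 comes from ignoring centres, and it persists after adjustment when residual clustering remains. What stands is the loss of precision and the uncorrected imbalance realised in this particular allocation. In addition, midwives enrolled women in allocated centres, so differences may not be due to chance alone; baseline adjustment deals with that only in part.
- **The gain can be overstated.** A reader might infer that adjustment makes good the whole planned 30% loss. Step 2 shows that this needs favourable conditions.
- **Adjustment would not make the comparison well powered.** This stands: for an effect near 1 point, power barely moves. The gain is worth having because it is cheap.
- **These are not primary outcomes.** The Outcomes section names only the alcohol biomarkers, and the sample size addresses only prevalence. This limits the weight of the point but does not remove it, since offspring neurodevelopment is a declared aim.

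**Conclusion.** The point holds as an improvement in precision and in handling imbalance for non-primary outcomes. The plan gives the offspring outcomes no analysis beyond generic crude tests, while adjusting ethanol intake and collecting baseline data that could serve both.

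The reduction in standard error is about 5-16% if centres do not differ. It is about 9-12% if centre means vary by 2-3 points and covariates explain 30% of within-centre variance. All of this rests on the assumed SD, R², centre variation and 4:4 split; the direction of the gain needs only that the covariates predict the outcome.

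It would be wrong to infer that the primary result is biased, or that covariate adjustment alone would make the offspring tests valid. Nothing here touches the primary comparison, and validity depends on a centre-level method that the Statistical analysis section does not contain.

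**What to change.** In the Statistical analysis section:

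1. For each offspring outcome, state a model with arm, child sex and a short fixed list of covariates measured before the first MI. Choose them from the items actually on the first-trimester questionnaire, plus SCL-90 and first-trimester AUDIT-C. The documents do not list the questionnaire items, so education or tobacco use can be named only if they were recorded. Do not use the post-delivery AUDIT-C.
2. Add exact gestational age at scan for neurosonography, and age at test for ASQ-3 and Bayley-III. Use a logistic model for FASD only if the counts allow.
3. State a centre-level method, either a mixed model or an analysis of centre summaries, with a small-sample correction for 8 centres (about 8 − 2 = 6 degrees of freedom).
4. Keep the crude difference as supportive.
5. State whether the 240 and 168 are all children or only exposed ones. Exposure is measured after allocation and may be changed by MI, and baseline adjustment does not repair selection on it.
6. Fix the list before offspring outcomes are examined by arm.

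The cost is wording and modest programming, with no new data. Gaps in covariates need simple imputation, and the list must stay short with so few centres.
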